4. ENDPOINTS

4.1. Primary endpoint

- Seropositivity status and anti-V1V2 (IgG, IgG1, IgG2, IgG3, and IgG4) binding antibody concentration as measured by BAMA at Y14, and at historical time points of study PRO HIV-002 (D0, D182, and D672).

Testing of samples for PRO HIV-002 time points will depend on availability of samples.

4.2. Secondary endpoints

- Magnitude, responder status, cytokine co-expression profile of HIV-1 specific CD4+ T cell and CD8+ T cell responses as assessed by ICS assay at Y14, and at historical time points of study PRO HIV-002 (D0, D98, and D672).
- Seropositivity status and anti-gp120 (IgG, IgG1, IgG2, IgG3, and IgG4) binding antibody concentration as measured by BAMA at Y14, and at historical time points of study PRO HIV-002 (D0, D182, and D672).

Testing of samples for PRO HIV-002 time points will depend on availability of samples.

Additional investigations, such as additional CMI parameters, memory B cell phenotypes and antibody function may be performed based on study results and availability of samples.

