10.5. Derived and transformed data

Demography

- Age at vaccination will be computed as the difference between the date of dose 1 administration in primary [PRO HIV-002](#) study and the 15 JUNE of the year of birth (only the year of birth will be collected). Age at Y14 visit in the study will be computed as the difference between the date of Y14 visit and the 15 JUNE of the year of birth. The ages will be expressed in years.
- For a given subject and a given demographic variable, missing measurements will not be replaced.

Safety

- For analysis of SAEs and for the analysis of concomitant medications, all subjects will be considered. Subjects who did not report an event or a concomitant GSK medication will be considered as subjects without the event or without the concomitant medication respectively.

Immunogenicity

- Any missing or non-evaluable immunogenicity measurement will not be replaced. The descriptive analysis performed for each assay at each time point will exclude subjects with a missing or non-evaluable measurement.
- The geometric mean titers (GMTs)/geometric mean concentrations (GMCs) will be computed by taking the anti-logarithm of the arithmetic mean of the log₁₀ transformed titers/concentrations.
- A seronegative subject will be defined as a subject whose antibody titer/concentration is below the cut-off value of the assay. A seropositive subject is a subject whose antibody titer/concentration is greater than or equal to the cut-off value of the assay.

- Vaccine response rates for HIV-1- specific CD4+ T-cells expressing **at least two markers** among CD40L, IL-2, TNF- α and IFN- γ with responders will be defined as subjects with:
 - a 2-fold increase as compared to the cut-off (limit of quantification [LOQ] of the assay), for subjects with pre-vaccination frequency below the cut-off;
 - at least 2-fold increase as compared to pre-vaccination frequency, for subjects with pre-vaccination frequency above the cut-off.

Other definitions of the CMI vaccine response might be explored during the analysis. They will be described in the SAP.

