10.7. Analysis of immunogenicity

The primary analysis will be performed on the PP cohort for immunogenicity and, if the percentage of vaccinated subjects with serological results excluded from the PP cohort for analysis of immunogenicity is at least 10%, a second analysis will be performed on the Total cohort.

For the humoral immune response

For anti-V1V2 and anti-gp120 (IgG, IgG1, IgG2, IgG3, and IgG4) antibody concentrations (by BAMA), at each time point [PRE(D0), PIV(D182), PIV(D672), PIV(Y14)] where such information is available:

- Seropositivity rates with 95% CIs will be tabulated.
- Geometric mean concentrations (GMCs) with 95% CIs will be tabulated and presented graphically.
- Geometric mean of ratios (GMR) of antibody concentrations at each post-vaccination time point [PIV(D182), PIV(D672), PIV(Y14)] over pre-vaccination [PRE(D0)] will be tabulated with 95% CI.
- Antibody concentrations post-vaccination will also be presented using reverse cumulative curves.

For the cell-mediated immune response

The following parameters will be summarised using descriptive statistics (N, GM, min, Q1, median, Q3, max) at each time point [PRE(D0), PIII(D98), PIV(D672), PIV(Y14)] where CMI results are available:

- Frequency of HIV-1 specific CD4+/CD8+ T-cells expressing **at least two markers** among CD40L, IL-2, TNF- α and IFN- γ as measured by ICS using PBMCs.
- Frequency of HIV-1 specific CD4+/CD8+ T-cells expressing **at least one marker** among CD40L, IL-2, TNF- α and IFN- γ as measured by ICS using PBMCs.
- Geometric mean ratios (GMR) of frequency of HIV-1 specific CD4+/CD8+ T-cells expressing **at least two markers** among CD40L, IL-2, TNF- α and IFN- γ at each post-vaccination time point [PIII(D98), PIV(D672), PIV(Y14)] over pre-vaccination (D0) will be tabulated with 95% CI.
- Vaccine response rates for HIV-1-specific CD4+ T-cells expressing **at least two markers** among CD40L, IL-2, TNF- α and IFN- γ .

These analyses will be further detailed in the SAP document.

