The BLI determined antigen-specific binding response, which is a reflective of the magnitude of antigen-specific antibodies in a sample, will be compared to gauge the difference in magnitude of antibody responses in participants' serum samples. The antigen-specific dissociation rate is indicative of the quality of the antibodies present in a sample. The antigen-specific binding response and dissociation rate data together can be used to rank the serum samples of study participants from different groups with a score that includes both the magnitude of the antibody response and the dissociation rate of the antibody-antigen complex as measured by BLI. The binding response, dissociation rate and avidity rank for each antigen will be used in statistical analysis as described in Analytical Plan section.

Cell-mediated immunity (CMI)

The role of CMI in the protective response to HIV is thought to be important for protection. The CMI response will be assessed on thawed PBMCs at CEVAC.

Detection of gp120, Nef and Tat, intracellular cytokine staining (ICS) technique

Intracellular cytokine staining (ICS) is a method providing information on the frequency of CD4+ and CD8+ T cells responding to the antigen and secreting molecules involved in immunity such as IFN- γ , IL-2, TNF-a and CD40-L. The assay will be performed on

thawed PBMCs. Briefly, PBMCs of the subjects are stimulated for 2 hours by the vaccine antigen and/or derived peptides. Then, intracellular block (Brefeldin A) is added to inhibit cytokine secretion for a subsequent overnight stimulation. The cells are then harvested and stained for cell surface markers (e.g. CD4 and CD8), to identify specific sub-populations of T cells. Subsequently, the cells are fixed and then treated with a detergent such as saponin to permeabilise the cell membrane. The cells are then incubated with fluorescently labelled, cytokine-specific or activation marker-specific antibody that forms complexes with the cytokine in the cytoplasm. The cytokine producing cells can then be detected by cytofluorometry. Results are expressed as a frequency of antigen-specific CD4+ or CD8+ T cells identified as expressing cytokine/marker upon the in vitro stimulation.

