6.4. Immunogenicity

6.4.1. Analysis of immunogenicity planned in the protocol

The primary analysis will be performed on the PP cohort for immunogenicity analysis and, if the percentage of vaccinated subjects with serological results excluded from the PP cohort for immunogenicity analysis is at least 20%, a second analysis will be performed on the Exposed Set.

For the humoral immune response

For anti-V1V2 and anti-gp120 (IgG, IgG1, IgG2, IgG3, and IgG4) antibody concentrations (by BAMA), at each time point [PRE(D0), PIV(D182), PIV(D672), PIV(Y14)] where such information is available:

- Seropositivity rates with 95% CIs will be tabulated.
- Geometric mean concentrations (GMCs) with 95% CIs will be tabulated and presented graphically.
- Geometric mean of ratios (GMR) of antibody concentrations at each post-vaccination time point [PIV(D182), PIV(D672), PIV(Y14)] over pre-vaccination [PRE(D0)] will be tabulated with 95% CI.
- Antibody concentrations post-vaccination will also be presented using reverse cumulative curves.

For the cell-mediated immune response

The following parameters will be summarised using descriptive statistics (N, GM, min, Q1, median, Q3, max) at each time point [PRE(D0), PIII(D98), PIV(D672), PIV(Y14)] where CMI results are available:

- Frequency of HIV-1 specific CD4+/CD8+ T-cells expressing **at least two markers** among CD40L, IL-2, TNF- α and IFN- γ as measured by ICS using PBMCs.
- Frequency of HIV-1 specific CD4+/CD8+ T-cells expressing **at least one marker** among CD40L, IL-2, TNF- α and IFN- γ as measured by ICS using PBMCs.

- Geometric mean ratios (GMR) of frequency of HIV-1 specific CD4+/CD8+ T-cells expressing **at least two markers** among CD40L, IL-2, TNF- α and IFN- γ at each post-vaccination time point [PIII(D98), PIV(D672), PIV(Y14)] over pre-vaccination (D0) will be tabulated with 95% CI.
- Vaccine response rates for HIV-1-specific CD4+ T-cells expressing **at least two markers** among CD40L, IL-2, TNF- α and IFN- γ .

Note: HIV-1-specific CD4+/CD8+ T-cells will be obtained by stimulating the PBMC samples with gp120.

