For the cell-mediated immune response

- Raw data available in the database (events/per million of cells) will be divided by 10 000 in order to express the results in percentage (%) in the output tables/graphs.
- The frequency of antigen-specific CD4+ or CD8+ T-cells producing at least 2 cytokines for each individual subject is calculated as the difference between the frequency of CD4+ or CD8+ T-cells producing at least 2 cytokines, upon in vitro stimulation with the antigen (induction condition) minus the frequency of CD4+ or CD8+ T-cells producing at least 2 cytokines upon in vitro stimulation in medium only (background condition).

$$Freq_{Induction}^{2+} = \frac{n_{Induction}^{2+} - n_{Background}^{2+}}{10\,000}$$

$n_{Induction}^{2+}$ = Number of antigen – specific CD4+/CD8+ T-cells (per million of cells) expressing at least 2 cytokines

$n_{Background}^{2+}$ = Number of CD4+/CD8+ T-cells (per million of cells) expressing at least 2 cytokines in the medium only

Values less than or equal to zero will be set to 1 for the purpose of geometric mean and standard deviation calculation and graphical representation.

Similar calculations will be used to estimate the frequency of HIV-1 specific CD4+/CD8+ T-cells expressing at least one marker.

- Co-expression profile of the HIV-1 specific CD4+ T-cells of each combination of the 4 markers (CD40L, IL-2, TNF- α and IFN- γ) will be presented graphically
- Vaccine response rates for HIV-1- specific CD4+ T-cells expressing **at least two markers** among CD40L, IL-2, TNF- α and IFN- γ with responders will be defined as subjects with:
 - a 2-fold increase as compared to the cut-off (=354, limit of quantification [LOQ] of the assay), for subjects with pre-vaccination frequency below the cut-off;
 - at least 2-fold increase as compared to pre-vaccination frequency, for subjects with pre-vaccination frequency above the cut-off.

Other definitions of the CMI vaccine response might be explored during the current analysis or after.

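### CD8+ responder status and co-expression are part of the secondary CMI endpoint, but both are planned for CD4+ only

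*SAP*

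**What the plan says.** The secondary CMI endpoint has the same wording in Protocol 10.2 and SAP 4.2: "Magnitude, responder status, cytokine co-expression profile of HIV-1 specific CD4+ T cell and CD8+ T cell responses as assessed by ICS assay". The secondary objective (Protocol 2.2, SAP 3.2) also names both cell types.

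The planned analyses are narrower.

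- **Magnitude.** Protocol 10.7 and SAP 6.4.1 summarise the frequency of cells with at least one and at least two markers for both cell types. They add the fold change over Day 0, where the SAP writes "Geometric mean ratios (GMR) of frequency of HIV-1 specific CD4+/CD8+ T-cells expressing". SAP 6.4.2 gives the background-subtracted derivation for both types and continues: "Similar calculations will be used to estimate the frequency of HIV-1 specific CD4+/CD8+ T-cells expressing at least one marker".
- **Responder status.** The definition in Protocol 10.5 opens "Vaccine response rates for HIV-1- specific CD4+ T-cells expressing", and the analysis bullet in Protocol 10.7 opens "Vaccine response rates for HIV-1-specific CD4+ T-cells expressing". SAP 6.4.1 and 6.4.2 keep the CD4+ restriction. For subjects below the cut-off before vaccination, SAP 6.4.2 requires "a 2-fold increase as compared to the cut-off (=354, limit of quantification [LOQ] of the assay").
- **Co-expression.** Protocol section 10 lists it as an endpoint component but plans no analysis of it. SAP 6.4.2 plans a graph: "Co-expression profile of the HIV-1 specific CD4+ T-cells of each combination of the 4 markers".

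SAP section 9 reports no changes from the planned analyses.

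**The concern.** The endpoint promises three things for each cell type, and the analysis text delivers all three only for CD4+. Nothing in either document explains the difference.

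The CD4+ wording does not read as shorthand. In SAP 6.4.1, three of the four CMI bullets name both cell types, and only the response-rate bullet names CD4+ alone. SAP 6.4.2 likewise names both types for the frequency calculations, then CD4+ alone for co-expression and response.

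A programmer who follows the SAP exactly would leave part of a stated secondary endpoint unreported. If someone asks for CD8+ response rates later, the rule and its cut-off would have to be chosen with the data already in hand.

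**Working it through.** The plan gives no figure to reproduce here. The check sets each endpoint component against every CMI analysis described in Protocol 10.5 and 10.7 and SAP 6.4.1 and 6.4.2.

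| Component | CD4+ | CD8+ |
|---|---|---|
| Magnitude | Planned (Protocol 10.7; SAP 6.4.1, 6.4.2) | Planned (same places) |
| Responder status | Planned (Protocol 10.5, 10.7; SAP 6.4.1, 6.4.2) | Not planned |
| Co-expression | Planned (SAP 6.4.2 only) | Not planned |

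**Count.** 3 components × 2 cell types = 6 parts. Planned: 3 for CD4+ and 1 for CD8+, so 4. Not planned: 6 − 4 = 2, both CD8+.

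**Outputs with no plan behind them.** Template 14 shows response rates at Day 98, Day 672 and Year 14, so a CD8+ counterpart has 3 time points. The note to Template 12 asks for 15 marker combinations at Day 0, Day 98, Day 672 and Year 14, so a CD8+ counterpart has 4.

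**Does planned CD8+ magnitude stand in for the missing parts?** No.

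- A geometric mean or a mean fold change does not give the proportion of subjects who still respond.
- The frequency of cells with at least two markers is a sum over combinations. It does not show which of the 15 combinations contribute.

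**Are the CD8+ data available?** Yes. Protocol Appendix A describes one ICS assay and states: "Results are expressed as a frequency of antigen-specific CD4+ or CD8+ T cells identified as expressing cytokine/marker upon the in vitro stimulation".

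**Is the CD8+ cut-off fixed?** No. The value 354 is called the LOQ of the assay, but it appears only in the CD4+ response rule and in the CD4+ Template 14.

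**What a CD8+ rate could say.** SAP 11.1 names the Clopper-Pearson interval. For x responders among n subjects, the lower limit is the 2.5% quantile of Beta(x, n−x+1) and the upper limit is the 97.5% quantile of Beta(x+1, n−x). For x = 0 the lower limit is 0 and the upper limit is 1 − 0.025^(1/n). The number of subjects with both a Day 0 and a post-vaccination result is not known. I assume 20, 30 or 40, around the planned total of approximately 30.

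| Responders / pairs (assumed) | Exact 95% CI |
|---|---|
| 0/20 | 0 to 16.8% |
| 0/30 | 0 to 11.6% |
| 0/40 | 0 to 8.8% |
| 3/30 | 2.1 to 26.5% |
| 15/30 | 31.3 to 68.7% |

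For example, 0/30 gives 1 − 0.025^(1/30) = 1 − 0.884 = 0.116. A CD8+ rate at Year 14 would therefore carry usable information even if no subject responded.

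**The case against.** The best case for the plan has five parts.

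1. **The documents leave room for more.** Both say other CMI response definitions might be explored, and SAP 4.2 allows additional CMI parameters. This does not close the gap. The clauses are optional and give no CD8+ rule. Protocol 10.5 says any such definitions will be described in the SAP, but SAP 6.4.2 describes none and leaves them to the analysis stage or later.
2. **The templates are illustrative, and the full table list (the TFL TOC) is a separate document not available here.** This is partly right. Templates 11 and 13 are also titled CD4+ only, although SAP 6.4.1 plans those analyses for both cell types, so the titles of Templates 12 and 14 prove nothing. The finding rests on the SAP body text, which an adapted title cannot widen. It remains possible that the table list includes CD8+ versions. What can be shown is that the SAP text does not plan them.
3. **The restriction may be deliberate.** Responder status is CD4+ in all four places where it is defined or planned, and the rationale describes strong earlier responses for CD4+ only. That is plausible, but then the endpoint wording is too broad and needs correcting.
4. **The objective does not require a responder rate, and CD8+ magnitude is well covered.** This stands, and it is why the point is minor. The endpoint, however, does name responder status for CD8+.
5. **The confidence intervals describe hypothetical results, and the cut-off matters only if CD8+ response rates are added.** Both stand. The size of the defect is 2 of 6 endpoint parts. The intervals only illustrate what would go unreported, and the cut-off belongs with the first remedy below.

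**Conclusion.** The concern holds. Two of the six parts of the secondary CMI endpoint, CD8+ responder status and CD8+ co-expression, have no planned analysis in either document. CD8+ magnitude is covered by frequencies for at least one and at least two markers and by the fold change over Day 0.

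The severity is minor. The study has one group, makes no hypothesis test and is descriptive, so no error rate or sample size is affected. The consequence is an incompletely reported secondary endpoint and no CD8+ responder rule set in advance.

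The count of 2 in 6 needs no assumption beyond reading the SAP body text as written. Only the illustrative intervals depend on assumed numbers of paired results.

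**What to change.** Either of two changes reconciles the text. One should be made before the analysis.

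- **Report the CD8+ parts.** In SAP 6.4.1 and 6.4.2, extend the response-rate and co-expression analyses to both cell types. Before analysis, have the laboratory confirm that 354 applies to CD8+ or supply another value, and state it in the SAP. Add CD8+ versions of Templates 12 and 14. The cost is small: SAP wording, one laboratory confirmation, and existing table and graph code rerun on data from the same ICS assay.
- **Narrow the endpoint.** If these CD8+ parts are not intended, limit responder status and co-expression to CD4+ in Protocol 10.2 and SAP 4.2, give the reason, and record the change in SAP section 9. This adds no outputs but needs a protocol change.

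The first route keeps the endpoint as stated and leaves the protocol's endpoint wording unchanged.

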5. ANALYSIS SETS

5.1. Definition

Note that in order to align to ICH and CDISC terminology the Total Cohort has been renamed Exposed Set (ES).

5.1.1. All enrolled subjects

The “All enrolled subjects” set will include all enrolled subjects with recorded data.

5.1.2. Exposed Set

The ES will include all subjects who signed the informed consent and provided a blood sample.

5.1.3. Per-protocol cohort for analysis of immunogenicity

The PP cohort for immunogenicity analysis will include all subjects from the ES:

- who meet all eligibility criteria,
- who present a negative HIV-RNA test at Y14.

Subjects eliminated from the PP cohort for immunogenicity analysis will have their results reported as line listings.

5.2. Criteria for eliminating data from Analysis Sets

Elimination codes are used to identify subjects to be eliminated from analysis. Detail is provided below for each sets.

5.2.1. Elimination from Exposed Set (ES)

Code 900 (invalid informed consent or fraud data) and code 1020 (Blood sample for immunogenicity tests [humoral and CMI] not available) will be used for identifying subjects eliminated from ES.

5.2.2. Elimination from Per-protocol (PP) cohort for immunogenicity analysis**5.2.2.1. Excluded subjects**

A subject will be excluded from the PP cohort for immunogenicity analysis under the following conditions

Code	Decode => Condition under which the code is used
900	Invalid informed consent or fraud data
1020	Blood samples for immunogenicity tests (humoral and CMI) not available
2010	Protocol violation (inclusion/exclusion criteria) => ineligible subject: 
 • A subject who has not received at least three doses of the gp120-NefTat/AS01B vaccine candidate in GSK Biologicals-sponsored PRO HIV-002 study • Other considerations as stated in section 4.2 – 4.3 in the protocol
2020	Initially HIV status positive or unknown => HIV-RNA result at Y14 positive or missing
2100	Serological results not available post-vaccination => all tests are missing at Y14
2120	Obvious incoherence or abnormality or error in data =>BS result available while BS not taken

5.3. Important protocol deviation not leading to elimination from per-protocol cohort

NA

6. STATISTICAL ANALYSES

Note that standard data derivation rule and stat methods are described in [Annex 1](#) and will not be repeated below.

6.1. Demography

6.1.1. Analysis of demographics/baseline characteristics planned in the protocol

For the ES and for the PP cohort for immunogenicity analysis, demographic data (age at vaccination in years, age at Y14 visit of this current LTFU study in years, gender and race) will be summarized using descriptive statistics:

- Frequency tables for gender and race.
- Mean, median, standard error for age.

6.1.2. Additional considerations

- Age at vaccination will be computed as the difference between the date of dose 1 administration in primary PRO HIV-002 study and the date of birth collected in that primary study (full date collected while only year of birth is collected in the current study). Age at Y14 visit in the study will be computed as the difference between the date of Y14 visit and the date of birth from study 002. The ages will be expressed in years.
- Summary statistics (Mean, median, standard error) of height and weight at the time of dose 1 administration will also be tabulated
- For a given subject and a given demographic variable, missing measurements will not be replaced unless they can be found in the primary PRO HIV-002 study.

6.2. Exposure

6.2.1. Analysis of exposure planned in the protocol

Not applicable

6.2.2. Additional considerations

Not applicable

6.3. Efficacy/Effectiveness

6.3.1. Analysis of efficacy planned in the protocol

Not applicable

6.3.2. Additional considerations

Not applicable

6.4. Immunogenicity

6.4.1. Analysis of immunogenicity planned in the protocol

The primary analysis will be performed on the PP cohort for immunogenicity analysis and, if the percentage of vaccinated subjects with serological results excluded from the PP cohort for immunogenicity analysis is at least 20%, a second analysis will be performed on the Exposed Set.

For the humoral immune response

For anti-V1V2 and anti-gp120 (IgG, IgG1, IgG2, IgG3, and IgG4) antibody concentrations (by BAMA), at each time point [PRE(D0), PIV(D182), PIV(D672), PIV(Y14)] where such information is available:

- Seropositivity rates with 95% CIs will be tabulated.
- Geometric mean concentrations (GMCs) with 95% CIs will be tabulated and presented graphically.
- Geometric mean of ratios (GMR) of antibody concentrations at each post-vaccination time point [PIV(D182), PIV(D672), PIV(Y14)] over pre-vaccination [PRE(D0)] will be tabulated with 95% CI.
- Antibody concentrations post-vaccination will also be presented using reverse cumulative curves.

For the cell-mediated immune response

The following parameters will be summarised using descriptive statistics (N, GM, min, Q1, median, Q3, max) at each time point [PRE(D0), PIII(D98), PIV(D672), PIV(Y14)] where CMI results are available:

- Frequency of HIV-1 specific CD4+/CD8+ T-cells expressing **at least two markers** among CD40L, IL-2, TNF- α and IFN- γ as measured by ICS using PBMCs.
- Frequency of HIV-1 specific CD4+/CD8+ T-cells expressing **at least one marker** among CD40L, IL-2, TNF- α and IFN- γ as measured by ICS using PBMCs.

- Geometric mean ratios (GMR) of frequency of HIV-1 specific CD4+/CD8+ T-cells expressing **at least two markers** among CD40L, IL-2, TNF- α and IFN- γ at each post-vaccination time point [PIII(D98), PIV(D672), PIV(Y14)] over pre-vaccination (D0) will be tabulated with 95% CI.
- Vaccine response rates for HIV-1-specific CD4+ T-cells expressing **at least two markers** among CD40L, IL-2, TNF- α and IFN- γ .

Note: HIV-1-specific CD4+/CD8+ T-cells will be obtained by stimulating the PBMC samples with gp120.

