5.7.3. Laboratory assays

Please refer to **APPENDIX A** for a detailed description of the assays performed in the study. Please refer to **APPENDIX B** for the address of the clinical laboratories used for sample analysis.

Test for the determination of HIV infection (to exclude subjects with HIV infection) will be performed at the Investigator’s laboratory using standardized and validated procedures. The diagnostic algorithm used in UZ Gent is: 4th generation screening test that detects antibodies and p24 antigen (VIDAS DUO). In case of reactivity, an Inno Lia confirmation test (Fujirebio) is performed. This test will allow to distinguish between a real seropositivity and a vaccine-induced seropositivity (if any). The result will be encoded in eCRF as a qualitative result (HIV infected: yes/no) and raw results will be uploaded into the study database.

Serological assays ([Table 5](#)) for the determination of antibodies against gp120 and V1V2 to check the subjects’ response to the vaccine they received in study [PRO HIV-002](#) will be performed at Duke Human Vaccine Institute using standardized procedures.

Table 5 Humoral immunity (Antibody determination)

System	Component	Method	Kit / Manufacturer	Unit	Cut-off *	Laboratory ***
SER	Human Immunodeficiency Virus Ab Anti-gp120** (IgG, IgG1, IgG2, IgG3, IgG4, and Total IgG Avidity)	BAMA	In-house	MFI	95 th percentile of the MFI-background-Neg from all baseline [†]	Duke Human Vaccine Institute
SER	Human Immunodeficiency Virus Ab Anti-V1V2** (IgG, IgG1, IgG2, IgG3, IgG4, and Total IgG Avidity)	BAMA	In-house	MFI	95 th percentile of the MFI-background-Neg from all baseline [†]	Duke Human Vaccine Institute

SER: serum; BAMA: Binding Antibody Multiplex Assay; MFI: mean fluorescence intensity

[†] Baseline is defined as Day 0 in [PRO HIV-002](#) study.

* Assay cut-off and unit might be subject to change during the course of the study (e.g., in case of requalification, revalidation or standardization). In this case, this will be documented in the clinical report.

** Performed on antigen corresponding to the vaccine strain (other HIV strains or HIV clades).

*** Refer to [APPENDIX B](#) for the laboratory addresses.

ICS (CFC) assays ([Table 6](#)) on HIV-1 specific CD4+ T cells and CD8+ T cells to check the subjects’ response to the vaccine they received in study [PRO HIV-002](#) will be performed at CEVAC using standardized procedures.

Table 6 Cell-mediated Immunity (CMI)

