9. SUBJECT COMPLETION AND WITHDRAWAL

Not applicable.

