10.4. Cohorts for Analyses

10.4.1. Total vaccinated cohort

The Total cohort will include all subjects who signed the informed consent and provided a blood sample.

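### The conditional second immunogenicity analysis has no rule removing subjects found HIV-infected at Year 14, so their values would be pooled as vaccine persistence

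*SAP*

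**What the plan says.** **Who is in the larger set.** Protocol 10.4.1: "The Total cohort will include all subjects who signed the informed consent and provided a blood sample". SAP 5.1.2 keeps the definition under a new name: "The ES will include all subjects who signed the informed consent and provided a blood sample". Neither mentions HIV status.

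**Who is taken out of it.** SAP 5.2.1 names two codes, 900 (invalid consent or fraud) and 1020 (no immunogenicity blood sample), which "will be used for identifying subjects eliminated from ES".

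**Where HIV status enters.** The PP cohort is limited to subjects "who present a negative HIV-RNA test at Y14" (SAP 5.1.3, as in protocol 10.4.2). The matching code, 2020, is defined as "HIV-RNA result at Y14 positive or missing". It appears only in the PP exclusion table (SAP 5.2.2.1) and in the PP block of Template 3. A breach of eligibility is code 2010, also PP-only.

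**When infection is detected.** Protocol 5.5 places consent, the eligibility check, the HIV test and the immunogenicity blood draws at one visit. Protocol 5.7.3 gives the purpose of the test: "Test for the determination of HIV infection (to exclude subjects with HIV infection) will be performed at the Investigator’s laboratory". It does not say from which set. Protocol section 9, on completion and withdrawal, reads "Not applicable".

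**When the larger set is analysed.** If the share excluded from PP reaches 20%, SAP 6.4.1 says that "a second analysis will be performed on the Exposed Set". Protocol 10.7 has the same rule for the Total cohort, with a threshold of 10%.

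**The concern.** The objective is persistence of a response to a vaccine given about 14 years earlier. At Year 14 the assays measure binding to HIV envelope antigens and T-cell responses to gp120. Nothing in their description separates a vaccine response from a response to infection. Protocol 5.7.3 recognises the distinction for the diagnostic test, whose confirmation step is meant to tell true seropositivity from vaccine-induced seropositivity.

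The PP cohort respects that distinction by requiring a negative HIV-RNA result. The second analysis reverses it, because it adds back PP-excluded subjects without looking at why they were excluded. A check on robustness to PP exclusions would then also contain a non-vaccine source of the measured response. A difference between the two analyses could not be read as either one.

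**Working it through.** There is no power or precision calculation to reproduce: protocol 10.3 takes the sample size from the parent study. The check is of the set rules first, then of the possible size.

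**1. Path of an infected subject under the rules as written**

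| Step | Rule | Result |
|---|---|---|
| Consents and is bled for immunogenicity | Protocol 10.4.1, SAP 5.1.2 | In the Exposed Set |
| HIV-RNA positive at Year 14 | Code 2020 | Out of PP only |
| Judged ineligible | Code 2010 | Out of PP only |
| Codes 900 and 1020 | Neither concerns infection | Stays in the Exposed Set |
| Second analysis triggered | Protocol 10.7, SAP 6.4.1 | Pooled |

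**2. How many exclusions trigger it**

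Count = share × N, rounded up, with N the subjects with serological results. Protocol 10.3 expects about 30 to 40 eligible subjects.

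- N = 30: 3 at 10%, 6 at 20%.
- N = 40: 4 at 10%, 8 at 20%.

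One infected subject (1/30 = 3.3%) does not trigger the analysis alone, but is pooled if other exclusions bring the total to the threshold.

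**3. Effect on the geometric mean (illustration)**

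Let k of N subjects be infected, each with a recorded value F times what it would otherwise have been. The mean log10 value rises by (k/N) × log10 F, so the geometric mean is multiplied by F^(k/N). If Day 0 is unchanged and the same N subjects have both results, the Year 14/Day 0 ratio is multiplied by the same factor. k and F are assumptions.

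| Infected (k) | N = 30, F = 10 | N = 30, F = 100 | N = 40, F = 10 | N = 40, F = 100 |
|---|---|---|---|---|
| 1 | 10^(1/30) = 1.08 | 100^(1/30) = 1.17 | 1.06 | 1.12 |
| 2 | 1.17 | 1.36 | 1.12 | 1.26 |
| 3 | 10^(3/30) = 1.26 | 100^(3/30) = 1.58 | 1.19 | 1.41 |

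At N = 30, three infected subjects alone reach the protocol's trigger but not the SAP's.

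**4. Effect on seropositivity (illustration)**

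An infected subject who would otherwise be seronegative adds 1/30 = 3.3 points. One who would be seropositive from vaccination anyway adds nothing. The effect therefore depends on the unknown Year 14 rate. Adding three infected, seropositive subjects to 27 others:

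- Assumed low rate: 5/27 = 18.5% becomes 8/30 = 26.7%, about 8 points.
- Assumed rate near the 87% that protocol 1.1 reports at 18 months after the last dose: 23/27 = 85.2% becomes 26/30 = 86.7%, 1.5 points.

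**The case against.** The strongest reply is that the primary analysis already deals with infection. It uses the PP cohort, which requires a negative HIV-RNA result, and PP-eliminated subjects are listed individually, so an infected subject is identifiable. This stands. A reader might infer that the main persistence estimate is contaminated; for HIV-RNA-positive subjects the documents show the opposite.

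Second, several conditions must coincide. Known infection is an exclusion criterion (protocol 4.3), so the subject must have an infection not known at entry, must have samples that are assayed, and enough subjects must be excluded to reach the trigger. This stands, and it limits the likelihood. A reader might also infer that infected subjects would themselves set off the second analysis. Under the SAP's 20% that takes six of 30, so other exclusions would normally be needed.

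Third, the stated purpose of the HIV test could mean that infected subjects leave the study altogether, and section 9 may only reflect a one-visit design. That is possible, but no set is named in 5.7.3 and no Exposed Set code implements it. The line listings do not fill the gap either: they cover every PP-eliminated subject, and those are the subjects the second analysis is meant to add back.

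Fourth, all analyses are descriptive (protocol 10.9, SAP section 7), and an all-subjects analysis has value because nobody is filtered out. No error rate is at stake. But a descriptive estimate offered as vaccine persistence should still describe that.

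**Conclusion.** The gap is real and narrow. As written, an infected subject who has been sampled enters the second immunogenicity analysis if it is triggered, and that subject's Year 14 values count as persistence. The problem is interpretability of a conditional, supportive table, not validity of the primary analysis.

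The size cannot be derived from the documents. With 30 subjects and an assumed 10 to 100-fold elevation, the Year 14 geometric mean concentration and the Year 14/Day 0 ratio inflate by 1.08 to 1.17 with one infected subject and by 1.26 to 1.58 with three. For seropositivity the shift is 3.3 points per infected subject who would otherwise be seronegative, and none for the rest.

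A reader might infer that every Year 14 result is biased upward. The documents do not support that. Seropositivity need not move, and they give no direction for the effect of infection on gp120-stimulated CD4+ and CD8+ results. Those values are equally unattributable to the vaccine, but the sign is uncertain.

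**What to change.** In SAP 6.4.1 and protocol 10.7, run the second immunogenicity analysis on the Exposed Set excluding subjects with HIV infection at Year 14. Define infection as a positive HIV-RNA result or infection confirmed by the protocol 5.7.3 algorithm.

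- **Use the same definition for the PP cohort** (protocol 10.4.2, SAP 5.1.3 and 5.2.2.1). PP now relies on HIV-RNA, while 5.7.3 is a serological algorithm. Filtering the second set on serology alone could drop an RNA-negative subject who remains in PP, or keep an RNA-positive subject whom PP removes. A shared definition keeps PP nested in the second set.
- **Do not filter on code 2020 as a whole.** It merges positive with missing HIV-RNA. Keep subjects whose result is only missing, provided the 5.7.3 algorithm does not confirm infection.
- **Report infected subjects' immunogenicity results in the line listings only**, and keep these subjects in the Exposed Set for demography and safety.

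The cost is a few sentences and a filter on data already planned: the HIV-RNA result (protocol Table 9) and the infection field in the eCRF (protocol 5.7.3). No new visit, sample or assay is needed. The downside is that the second analysis may lose a few subjects and will no longer strictly cover everyone sampled, which its title should state.
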